UAB Research Pharmacy
UAB Hospital Investigational Drug Service Pharmacy
[name]
[name]
[contact]
[contact]

Changes between Amendment 11 version 2.8 dated 20 Jan, 2021 and Amendment 12 version 2.9 dated 20 Sep 2021

Section/location	Change	Rationale
8	
 • Adding an unscheduled visit 	Administrative change
Study synopsis	
 • In a previous amendment it was stated that 4-20 participants are to be enrolled and treated in addition to the first 4 in the seed model (Section 4.1.2). The enrollment number is being increased to 24 to clarify that the previously stated 4-20 participants are in addition to the first 4. 	Administrative change

STUDY SYNOPSIS

Objective:	To obtain safety information in small cohorts of individuals (three patients per group), with cohorts to receive escalating doses of M032. Safety will be assessed at each dose level before proceeding to the next dose. Biologic secondary objectives include characterization of the in situ activity of M032 after intratumoral inoculation and of the local and systemic immune responses to M032. As a clinical secondary objective, patients will be followed serially by MRI for potential clinical response to M032. The clinical strategy takes advantage of the virus' ability to infect and lyse tumor cells and the potential for enhancement of this effect by the induction of an anti-tumor immune response by IL-12 as well as an anti-angiogenic response by this cytokine.
Treatment Indication:	Progressive growth of glioblastoma multiforme , anaplastic astrocytoma or gliosarcoma after radiation therapy.
Clinical Phase:	Phase 1 (open-label)
Design:	Single dose of M032 infused through catheters into region(s) of tumor defined by MRI; Up to 3 patients/dosage level; dosage escalation proceeds only after a minimum of 24 days of observation, if incidence of Grade III/IV toxicities is acceptable. Dose increases or reductions will be determined using a modified Continual Reassessment Method (CRM); extent of dose changes for subsequent subjects will be increased up to, but not exceeding the next higher dose level (1 log). Dose modifications will utilize a modified CRM for each successive subject until an MTD or the maximal planned dose is reached.
Study Duration Per Patient:	12 months

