Three values for d_{90} will be chosen in this protocol with weights of one tenth that of real subject data. This allows flexibility in the upper end of the dose toxicity curve. This adaptation to the CRM came about after subject data demonstrated that d_{90} was incorrect in previous studies, because doses approaching d_{90} were tried with no toxicities observed. This situation required that d_{90} be moved to a higher dose or the fitted dose toxicity curve became too steep and no dose escalations resulted.

We assume the dose for $d_{10} = 1 \times 10^4$ pfu for M032 (**Table 1**). A set of three values will be chosen for $d_{90} = 1 \times 10^{15}$ pfu. These values for d_{90} spread probability mass over a wider range and may eliminate the need to increase d_{90} if the data are inconsistent with a single value. Based on these starting points, our desire is to employ a dose of virus to yield no more than 33% chance of clinical toxicity. The initial starting dose will be assumed to be 1×10^5 PFU and the maximum dose to be tested would be 1×10^9 PFU. Further assumptions would be that the maximum number of subjects would be 204 and that the dose cohort size would be 1. Further, the next CRM recommended log dose would be rounded to the nearest 0.5 or full dose. Moreover, the number of consecutive subjects at the maximum tolerated dose would be 10 or a number until 20 subjects are treated, whichever comes first. This will allow us to collect more information of the safety of the MTD. If a second toxicity is observed for patients on the highest dose, then the next lower dose is used and declared MTD if 10 consecutive subjects on the same dose are toxicity free or if n=20 is reached. If more toxicities are found, CRM will be used in the de-escalation of the dose.

The outcome space for the first CRM iterations would look like the values shown as six sample scenarios in **Table 2** using a starting dose 1×10^5 pfu. We will not allow dose escalations to exceed 10 times the maximum dose already administered. In this way, we prevent a too rapid dose escalation or testing high doses without a reasonable degree of certainty concerning their safety. Although the values in **Table 2** appear reasonable to us currently, we emphasize that they should not be taken literally. Indeed, if we receive approvals (DSMB, IRB, FDA), we will update the CRM model using the four patients previously enrolled and treated. Some of the data

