Table 1: Initializing Data used to start the CRM			
Log Dose	N	r	Weight
4	1	0.05	0.5
5	1	0.10	0.5
6	1	0.2	0.5
7.5	1	0.5	0.5
9	1	0.8	0.5
10	1	0.9	0.5
12	1	1	0.5
15	1	1	0.5

(Initial recommended dose based on these data=6.7842)

$$L(\beta, d_{50}) = \sum_{i=1}^k \left[\log \binom{n_i}{r_i} - n_i \log(1 + e^{-\beta(d_i - d_{50})}) - (n_i - r_i) \log(1 + e^{-\beta(d_i - d_{50})}) \right]$$

could suggest that the current value for d_{10} and/or d_{90} is inappropriate. We would not proceed blindly with a CRM (or any other) dose escalation in such a circumstance. All testing doses will be the estimated dose round-down to the nearest 10th.

For each subsequent level, the investigators will evaluate the recommended dose-level. It is possible that the model may recommend large interval increases in dose level with which the investigators do not feel comfortable. In these cases, the investigators will use this information and their best clinical judgment to assign a next dose level. We emphasize that the dose levels recommended by the CRM should not be taken literally.

Model based dose escalation methods, especially the CRM, are able to account for ordinal or quantitative toxicity assessments, and use this information to guide subsequent dose changes. In particular, the binomial likelihood is

where i indexes the dose level, p is the probability of toxicity (equation 1 above), d is dose, n the number of subjects treated at each dose, and r the number of toxicities. While n is constrained to be an integer, r does not have to be integral. In particular, r can be taken to be the sum of ordinal or quantitative toxicity measures provided that $r < n$. The maximization of equation 2 with respect to the parameters (model fitting) can then proceed in the usual fashion. Furthermore, the ordinal scores need not be the same for all types of toxicity. For example, we might not want alopecia to have the same effect on dose reduction as neurologic toxicities.

Table 2: Six Different CRM-defined Dose Escalation Scenarios

Subject #	S1	S2	S3	S4	S5	S6
1	5	5	5	5	5	5
2	6	6	6	6	6	6
3	7	7	7	7	7	7
4	7.5	7.5	7.5	7.5	7.5	7.5
5	8	8	8	8	8	8
6	8	8	8	8	8	8
7	8.5	8.5	8.5	8.5	8.5	7.5
8	9	9	9	9	8	8
9	9	8.5	9	9	8.5	8
10	9	8.5	9	9	8.5	8
11	9	8.5	9	8	8.5	8.5
12	9	8.5	9	8.5	9	8.5
14	9	8.5	9	8.5	9	9
15	9	8.5	9	8.5	9	9
16	9	8.5	9	8.5	9	9
17	9	8.5	8.5	8.5	9	9
18	9	8.5	8.5	8.5	9	9
19		8.5	8.5	8.5	9	9
20			8.5	8.5	9	9
MTD	9	8.5	8.5	8.5	9	9

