4.1.2 Estimated Number of Patients

Moving forward, we anticipate as few as four and as many as 20 additional patients could be enrolled and treated in this trial. We expect approval of the use of the four already enrolled and treated patients to seed the model, which would bring the overall total range from 8- 24 patients. If the highest planned dose is successfully administered to subjects and assuming one subject per CRM-calculated dose level (10), and an additional 10 subjects will be entered at the CRM-estimation of the safe target dose ($10+10 = 20$). If all subjects develop DLTs, the CRM model would de-escalate both through the initial and the two lower dose levels involving no more than 4 subjects and the trial would be halted (Section 4.5) with a minimal accrual of 4 subjects. Assuming that no DLTs will be encountered, we expect that under optimal conditions only 20 subjects ($10+10$) will be enrolled and treated in this study. These numbers will be modified if the new patient data for seeding the model is approved and could even decrease.

Thus, the maximum number of subjects that we expect to enroll and treat in this trial would be 20, assuming that the CRM will adjust each dose after the first 2 or 3 subjects and as more subjects are enrolled to encompass the initial test range. On the other hand, the minimum number of subjects who could be enrolled in this trial would be 4 assuming 2 DLTs at Dose Level 1, and the CRM recommending one or two lower doses.

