There will be a minimum twenty-four (24) day observation period between the first patient at each dose level and subsequent patients enrolled to allow for evaluation of potential toxicity. If no dose-limiting toxicity is seen with the first patient, the twenty-four day waiting period will be waived for the second and third patients at that dose level. If the incidence of DLT at any given dose level meets the criteria for dose escalation, there will be a waiting period of a minimum of 24 days before dose escalation occurs. The Medical Monitor, in conjunction with a duly chartered external Data and Safety Monitoring Board comprised of an Infectious Disease expert, a neurosurgeon familiar with oncolytic virus therapy, a neuro-oncologist familiar with oncolytic virus therapy and an expert in the use of molecular biology methods to detect and quantify Herpes Simplex Viruses in clinical

specimens, will evaluate the safety of each dose tested to determine whether the protocol may proceed to the next dose level.

CTCAE#	Body System	Event name	Definition of Grade 3 Toxicity	Rationale for inclusion
222	General disorders and administration site conditions	Gait disturbance	Disabling; limiting self care ADL	Many subjects with malignant glioma have gait disturbance as a result of chronic corticosteroid administration
494	Musculoskeletal and connective tissue disorders	Muscle weakness left-sided	Limiting self care ADL; disabling	Malignant glioma can produce muscle weakness due to interruption of motor function
495	Musculoskeletal and connective tissue disorders	Muscle weakness lower limb	Limiting self care ADL; disabling	Malignant glioma can produce muscle weakness due to interruption of motor function
496	Musculoskeletal and connective tissue disorders	Muscle weakness right-sided	Limiting self care ADL; disabling	Malignant glioma can produce muscle weakness due to interruption of motor function
498	Musculoskeletal and connective tissue disorders	Muscle weakness upper limb	Limiting self care ADL; disabling	Malignant glioma can produce muscle weakness due to interruption of motor function
527	Nervous system disorders	Ataxia	Severe symptoms; limiting self care ADL; mechanical assistance indicated	Malignant glioma itself and many of the anti-epileptics drugs used to treat seizures associate with this disease can produce ataxia that requires mechanical assistance

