11. STATISTICAL CONSIDERATIONS

We will implement the CRM design (the dosing range is described previously in this protocol) in a manner similar to that of Geletneky et al. [43] We will define the primary criterion for dose modification as the relative frequency of a DLT at a given dose level. A dose will be considered as tolerable if the probability of toxicity is ≤33%. The Recommended Phase 2 Dose (RP2D) will be the dose level with the highest posterior probability of having a toxicity of ≤33%. The Optimal Biologic Dose (OBD) will be the RP2D that is obtained by enrolling the fewest number of evaluable patients possible. The posterior probability for toxicity will be determined using a logistic model, where the toxicities will be parameterized as probabilities in the model. When a patient enters the study, the dose level will be determined by calculating the posterior probability for each dose level to be tolerable. The highest dose level that is tolerable will be allocated. Regarding the dose escalation scheme, a conventional three-at-one [44] design will be used as long as no DLT is observed. After the first DLT is observed, one additional patient will be enrolled at the same dose before the dose will be determined as the RP2D using the logistic model. The highest dose with a median probability of at least 33% will be applied as the current RP2D to the subsequent patient, following the CRM [45]. If the RP2D is calculated as dose level -1 (i.e. 1×10^4 PFU), the trial will end with no safe dose established.

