APPENDIX D
INSTRUCTION FOR M032 DOSE PREPARATION
 FOR GMP LOT 0909005 ONLY
 6 hr Infusion Only

Summary:

The following protocol for preparation of different doses of M032 for infusion is provided for informational purposes only and describes the methods used in preparing doses at 1 log intervals, beginning at the starting dose of 1×10^5 PFU delivered in the total volume of 2.4cc. The Continual Reassessment Method (CRM) will estimate the exact dose to be administered to each subsequent subject in 2.4cc. This calculation will be made once each subject has met the 24 day interval and all relevant events have been recorded. A subject- and dose-specific protocol will be prepared and provided to the Trial PIs, the Research Nurse (Study Coordinator) and the Research Pharmacist within a 24 hour period to ensure adequate time to review and approve, before that next subject is enrolled in the study.

Stock Virus:	3.32E+09 per cc	0.5 cc/vial	1.66E+09 per vial
Infusion Rate/Catheter:	0.1 cc/hr	Number of Catheters:	4
Total Rate:	0.40 cc/hr	Infusion Time:	6 hrs
Total Infusion Volume:	2.4 cc	Infusion Dead Space:	4.5 cc

Intermediate Virus Dilution:		Volume	Concentration	
	Stock Virus		0.5 cc/vial	
	Diluent		3.4 cc	
	[Final]	2.4 cc =	3.9	4.26E+08 pfu/cc
			1.02E+09 PFU	Total

Desired Dose and Concentration

Dose (PFU)	Concentration			
1.00E+05	4.17E+04 per cc	Virus (cc)	Diluent (cc)	Concentration (PFU/cc)
Intermediate Virus Dilution		1	9	4.26E+07
4.26E+07 Virus Dilution		1	9	4.26E+06
4.26E+06 Virus Dilution		1	9	4.26E+05
4.26E+05 Virus Dilution		8	72	4.26E+04
		2.4 cc =		1.02E+05 PFU, final dose

1.00E+06	4.17E+05 per cc	Virus (cc)	Diluent (cc)	Concentration (PFU/cc)
Intermediate Virus Dilution		1	9	4.26E+07
4.26E+07 Virus Dilution		1	9	4.26E+06
4.26E+06 Virus Dilution		8	72	4.26E+05
		2.4 cc =		1.02E+06 PFU, final dose

1.00E+07	4.17E+06 per cc	Virus (cc)	Diluent (cc)	Concentration (PFU/cc)
Intermediate Virus Dilution		1	9	4.26E+07
4.26E+07 Virus Dilution		8	72	4.26E+06
		2.4 cc =		1.02E+07 PFU, final dose

1.00E+08	4.17E+07 per cc	Virus (cc)	Diluent (cc)	Concentration (PFU/cc)
Prepare an intermediate Virus Dilution using 2 Vials (1.0 cc) diluted in 6.8 cc Diluent = 7.8 cc				
Intermediate Virus Dilution		6	54	4.26E+07
		2.4 cc =		1.02E+08 PFU, final dose

This Dose will involve Diluting 14 vials of M032 (7 ml) in the defined diluent volume to produce the required concentration in 2.4 ml

Dose	Concentration			
1.00E+09	4.17E+08 per cc	Virus, cc	Diluent, cc	

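### The protocol gives two incompatible escalation schemes and two rounding rules, so the next dose is not fixed, and the maximum of 20 additional patients (24 in all) is derived only for one subject per level

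*Combined protocol and SAP*

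**What the plan says.** **Cohort size.** Section 4.1.1 assumes that "the maximum number of subjects would be 204 and that the dose cohort size would be 1". Table 2 moves one subject at a time, and Section 4.1.2 counts one subject per model-derived level. Section 11 says that "a conventional three-at-one [44] design will be used as long as no DLT is observed". Section 4.2 refers to second and third patients at a level. The synopsis carries both ideas. Its objective begins "To obtain safety information in small cohorts of individuals (three patients per group", and its design row allows up to three patients per level but applies the continual reassessment method (CRM) to every successive subject.

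**Waiting.** Appendix D says of the CRM dose for each subsequent subject: "This calculation will be made once each subject has met the 24 day interval". Section 4.2 says that, if the first patient has no dose-limiting toxicity (DLT), "the twenty-four day waiting period will be waived for the second and third patients at that dose level".

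**Rounding.** Section 4.1.1 says "the next CRM recommended log dose would be rounded to the nearest 0.5 or full dose" and later "All testing doses will be the estimated dose round-down to the nearest 10th". The second rule gives no unit.

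**Maximum number.** Section 4.1.2 adds 10 single-subject levels to 10 at the target dose to reach 20, calls these additional patients, and adds the four already treated to reach 24. The synopsis (8 to 24) and Section 11.2 (20 additional) agree. Section 4.1.2 also states "Thus, the maximum number of subjects that we expect to enroll and treat in this trial would be 20". Section 4.1.1 gives 204, then uses 20 twice in its rule for stopping at the maximum tolerated dose (MTD). Section 4.2 stops enrolment once six patients tolerate the maximal planned dose.

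**The concern.** In a dose-finding trial, the rule that turns accumulated data into the next dose is the design. Here two people who both follow the protocol could give the next subject different doses and wait different times before doing so. The dose path, the number treated at the final dose and the operating behaviour shown in Table 2 all depend on which section is followed.

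The safety rules depend on it too. Several halting rules in Section 4.5 act on two or more toxicities in the same dose cohort. If a cohort is one subject, such a rule can never involve two subjects, unless cohort there means everyone treated at a dose level.

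**Working it through.** **1. The plan's own maximum.** From Section 4.1.2: 10 + 10 = 20 additional, and 20 + 4 = 24. Both reproduce, on the one-subject reading. The first 10 is not derived. From log 5 to log 9 there are 5 full-log levels or (9 − 5)/0.5 + 1 = 9 half-log levels. The same section also explains 20 by an adjustment after the first two or three subjects, which is a different cohort size.

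**2. One subject at a time, no DLT.** Scenario S1 of Table 2 has 7 subjects below log 9 and 10 at log 9, so 17 printed rows (the numbering skips 13).

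I refitted the two-parameter logistic model to the Table 1 pseudo-data. Settings were weight 0.5 for pseudo-data, weight 1 for real subjects, target 0.33, start at log 5, steps of at most 1 log and a ceiling of log 9. Log 9 is first reached at:
- subject 8 with nearest-half rounding, so 7 + 10 = 17;
- subject 9 with rounding down to 0.1 log, so 8 + 10 = 18.

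Both fit within 20.

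**3. Three per level on the five full-log levels, no DLT.** Four levels lie below log 9, so 4 × 3 = 12 subjects come first.

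| Reading of the final stage | Total |
|---|---|
| Stop at six on the maximal dose (Section 4.2) | 12 + 6 = 18 |
| Top cohort counts toward the ten | 12 + 10 = 22 |
| Ten are extra to the top cohort | 15 + 10 = 25 |
| 20-subject limit in Section 4.1.1 binds | 12 + 8 = 20, only 8 at the top dose |

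With the model refitted after every three subjects, both rounding rules reach log 9 at subject 16. That gives 15 + 10 = 25, or 15 + 6 = 21 under the six-patient rule.

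**4. The second subject's dose.** After a DLT-free first subject at log 5, Table 2 gives log 6. Three per level gives log 5. The difference is 10-fold.

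**5. Rounding.** Assume that the tenth is 0.1 log. The protocol prints an initial recommendation of 6.7842. It illustrates the rounding only, since dosing starts at log 5.
- Nearest half: 7.0, or 1.0 × 10^7 PFU.
- Round down to a tenth: 6.7, or 5.0 × 10^6 PFU.
- Ratio: 10^0.3 = 2.0.

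Nearest-half minus round-down runs from −0.2 to +0.3 log, so neither rule is always the lower one. In the refit, the estimate after three DLT-free subjects is 7.614. This rounds to 7.5 under the first rule and 7.6 under the second. Subjects 4 to 8 then receive:
- nearest half: 7.5, 8.0, 8.5, 8.5, 9.0;
- round down: 7.6, 7.9, 8.3, 8.6, 8.9.

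A side remark: I could not reproduce 6.7842 from Table 1 at the stated target. The refit gives 6.691 at 33%, 6.707 at one third and 6.788 at 35%. I use the printed figure as it stands, but the target set in the software should be confirmed.

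**6. The 204.** At the 10 to 12 patients per year in Section 11.2, 204 would take 204/12 = 17 to 204/10 = 20.4 years. Section 4.1.1 itself uses 20 in the sentences that follow.

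**The case against.** The strongest reply is that the sample size is sound. Section 4.1.2 shows its derivation, the synopsis and Section 11.2 agree with it, and 20 and 24 are one figure without and with the first four patients. That stands. A reader might infer that 20 or 24 does not follow from the plan at all, or that 204, 20 and 24 are three competing caps. The documents do not support either reading. The 204 is most likely a merged edit of 20 and 24, though that is an inference.

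A reader might also infer that three-subject cohorts would push enrolment to 25, or even to 9 × 3 + 10 = 37. The 25 is only the top of a range. The 37 matches no design described: half-log rounding is stated alongside a cohort size of one, and Table 2 never visits 5.5 or 6.5. If the 20-subject limit binds, larger cohorts shrink the group at the top dose and do not raise enrolment.

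On rounding, Table 2 uses only half-log values, which fits the first rule, and the unit of the second is unstated. If the tenth referred to the leading figure of the PFU dose after half-log rounding, the two rules could be applied in turn and the gap would largely vanish. The text does not say so. Section 4.1.1 also lets investigators override the model. That discretion does not repair a rule whose default output is undefined.

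**Conclusion.** The point holds for the escalation scheme, the waiting rule and the rounding rule. These are current statements that cannot all be followed as written, and they change the dose: 10-fold for the second subject between the two cohort schemes, and up to 2-fold between the rounding rules if the tenth means 0.1 log. Neither rounding rule is consistently the more cautious.

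For the sample size the conclusion is narrower. The figure of 20 additional (24 in all) rests on one subject per level and on a count of ten levels that the dose range does not give. It is not derived for three per level, where the DLT-free total is 18 to 25 depending on the reading, or 20 with 8 at the top dose if the limit binds. Whether 20 means additional patients or all patients is not consistent within Sections 4.1.1 and 4.1.2.

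The modelled paths assume no DLT and the Table 1 weights. The contradictions themselves rest on no assumption beyond the unit of the tenth.

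**What to change.** Reconcile the synopsis, Section 4.1.1 with Table 2, Section 4.1.2, Section 4.2, Section 11 and Appendix D to one cohort size, one waiting rule and one rounding rule with its unit. Which of the stated rules to keep is for the sponsor and its safety board; this review does not choose. Then:

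- Check that the halting rules in Section 4.5 that refer to the same dose cohort still work under the chosen cohort size, and define cohort there.
- Correct 204.
- State in Sections 4.1.1 and 4.1.2 that 20 means additional patients, if that is intended.
- Settle whether the final stage is six patients, ten including the first arrivals, or ten more.
- Recompute 10 + 10 and Table 2 under the reconciled design, and confirm the toxicity target used by the software.

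The cost is an amendment of wording, a recount and a rerun of the scenarios. If three-subject cohorts are kept, either the stated maximum or the number treated at the final dose may change.

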Subject Population:	8 to 24 patients with recurrent/progressive glioblastoma multiforme , anaplastic astrocytoma or gliosarcoma depending on toxicities. (Numbers may vary slightly pending acceptance of previously treated patients to update the CRM)
Study Medication and Dosage:	Dose escalations of up to, but not exceeding the next highest dose level (1 log). Dose escalations from 1×10^5 to 1×10^9 plaque-forming units of M032, a genetically engineered herpes simplex virus type 1 expressing human IL-12 (NSC 733972).
Safety Evaluations:	Follow-up evaluations using routine laboratory analyses and clinical measurements of neurological function and evidence of M032-related toxicity. Studies to evaluate the possibility of M032 shedding will also be conducted. Patients will be observed closely during the planned post-treatment hospitalization period, followed by outpatient evaluations done at 10 days, then months 1, 2, 3, 4, 5, 6, 9 and 12, subject to disease progression.
Study Endpoints	Primary: CRM-estimated highest safe dose or maximal planned dose if no dose-limiting toxicity observed. Secondary: Time to progression, survival, biologic assessments.

TABLE OF CONTENTS

Section	Page Number
SYNOPSIS	3
1. OBJECTIVES	6
1.1 Lay Abstract	6
1.2 Primary Objective	6
1.3 Secondary Objectives	6
1.4 Tertiary Objectives	6
2. BACKGROUND	6
2.1 Safety and efficacy of non-virulent, oncolytic $\Delta\gamma$134.5 HSV	6
2.2 Malignant Glioma	10
2.3 Rationale	11
3. PATIENT SELECTION	11
3.1 Eligibility Criteria	11
3.2 Exclusion Criteria	12
3.2 Inclusion of Women and Minorities	13
4. TREATMENT PLAN	13
4.1 Study Summary	13
4.2 Definition of Dose-Limiting Toxicity	18
4.3 Supportive Care Guidelines	20
4.4 Duration of Therapy	20
4.5 Halting Rules for Study	20
5. EXPECTED ADVERSE EVENTS/DOSE MODIFICATIONS	21
5.1 Expected Adverse Events Associated with M032	21
5.2 Dosing Delays/Dose Modifications	23
5.3 Adverse Assessment and management Assessment by PI/Clinician	23
6. AGENT FORMULATION AND PROCUREMENT	23
6.1 M032 Formulation and Storage	23
6.2 Availability	23
6.3 Excipient for Dilution of M032	24
6.4 M032 Dose Preparation	24
6.5 Precautions in Handling M032	24
6.6 Precautions in Disposal of M032	24
7. CORRELATIVE/SPECIAL STUDIES	24
8. STUDY CALENDAR	26
8.1 Study Procedures	27
9. MEASUREMENT OF EFFECT	33

9.1	Definitions	33
9.2	Guidelines for Evaluation of Measurable Disease	33
9.3	Response Criteria	34
9.4	Confirmatory Measurement/Duration of Response	35

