(yellow cells= maximum tolerated dose (MTD); magenta cells =toxicity; white cells=no toxicity)

As subjects are treated at doses estimating the true MTD, the recommended subsequent dose levels will begin to converge. The criteria to declare the MTD will be when 2 recommended doses are within 10% of one another. It is possible that the dose escalation could continue indefinitely and that the MTD is not reached. If 10 subjects are treated in the full dose range in this dose-finding study and the MTD has not been reached, we will take pause, evaluate the data in consultation with the DSMB, and determine whether to continue the dose-escalation or terminate the Phase I portion of the study. If a MTD is not being reached based on clinical toxicities (too many or too few), the biological indicator (increased PFS or OS) may factor in the choice of the M032 dose for the ultimate planned phase II trial.

A maximum of 10 subjects will be treated at the putative MTD to have better estimation of $\leq 33\%$ DLT rate.

No enrollment of special or vulnerable populations is anticipated.

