4.2 Definition of Dose-Limiting Toxicity

The Cancer Therapy Evaluation Program (CTEP) has published Common Terminology Criteria for Adverse Events, version 4.0 for the grading of adverse events experienced in clinical trials for anti-neoplastic agents. Any grade 3 or greater non hematologic toxicity as defined by NCI CTCAE v 4, and considered as being possibly, probably or likely related to M032 will be considered a Dose Limiting Toxicity (DLT). However, specific symptoms including seizures, neurologic deficits such as weakness, dysphasia or sensory loss are prominent in this patient population due to the fact that these tumors frequently disrupt the function of normal areas of eloquent brain. Neurologic symptoms from involvement of eloquent brain are commonplace; corticosteroid, radiation, and chemotherapies also produce pre-existing symptoms in almost all cases. The pre-existing conditions listed in the **Table** on the following page are acceptable for inclusion in the clinical trial, provided the subjects meet the other inclusion and exclusion criteria.

For all of these pre-existing conditions, DLTs will be defined as progressive involvement of neurological dysfunction not attributable to tumor progression and/or the development of life threatening symptomatology associated with the original baseline status.

Neurologic deterioration will not be considered dose-limiting if it resolves back to the patient's baseline within two weeks of completing treatment. For example, increased weakness or aphasia that occurs during the infusion will be treated with increasing steroid doses and/or slowing of infusion rates, but not treated as a DLT if symptoms improve to baseline within fourteen days of completing treatment. Because of the site of M032 inoculation, important additional events that will be considered dose-limiting toxicities if they are likely related to M032 include death, stroke, hematoma requiring surgery, untreatable neurologic deterioration, unresponsive systemic infection, and disseminated HSV infection.

Management of the above adverse events is outlined in **Section 5**.

The maximally tolerated dose (MTD) is the highest dose level below the maximally administered dose when dose escalation decisions are made according to the guidelines above. Enrollment will be stopped when the MTD is determined or the maximally planned dose is acceptably tolerated by six patients.

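### The rules for declaring the MTD conflict: the 10% convergence rule has no scale, rounding or precedence and is met below every MTD in Table 2, and Section 4.2 disagrees on both the maximal dose and the number of subjects

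*Combined protocol and SAP*

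**What the plan says.** The plan gives the following rules and examples.

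- **Convergence (Section 4.1.1, after Table 2).** "The criteria to declare the MTD will be when 2 recommended doses are within 10% of one another". The same section then says "A maximum of 10 subjects will be treated at the putative MTD".
- **Run length or cap (Section 4.1.1, before Table 1).** "the number of consecutive subjects at the maximum tolerated dose would be 10 or a number until 20 subjects are treated, whichever comes first". After a second toxicity at the highest dose, the next lower dose is "declared MTD if 10 consecutive subjects on the same dose are toxicity free or if n=20 is reached".
- **Definition (Section 4.2).** "The maximally tolerated dose (MTD) is the highest dose level below the maximally administered dose", subject to the escalation guidelines. Section 11.1 sends the reader to Section 4.2 for the definition of the MTD.
- **Enrolment stop (Section 4.2).** "Enrollment will be stopped when the MTD is determined or the maximally planned dose is acceptably tolerated by six patients".
- **Primary endpoint (Study Synopsis).** "CRM-estimated highest safe dose or maximal planned dose if no dose-limiting toxicity observed".
- **Sample size (Section 4.1.2).** Built as 10 + 10 = 20, the second 10 being treated at the dose the CRM estimates as safe.
- **Rounding (Section 4.1.1).** One sentence rounds the recommended log dose to the nearest half log. Another, below Table 1, rounds the tested dose down to the nearest tenth.
- **Worked example (Table 2).** Six dose paths, with MTDs of 9, 8.5, 8.5, 8.5, 9 and 9 on the log10 scale.

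**The concern.** The MTD is the primary result of this trial. Section 4.1.1 states one criterion for declaring it and illustrates a different one in Table 2. Section 4.2 then adds a definition and a stopping count that fit neither fully. No sentence says which prevails.

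Section 4.2 also closes enrolment once the MTD is determined. A convergence rule that is met early can therefore end the trial, not merely label a dose. Two teams applying the document in good faith could stop at different subjects and report different MTDs from the same outcomes.

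**Working it through.** **1. Which rule reproduces Table 2?** The table prints row labels 1 to 20 without 13, so runs are counted in printed rows.

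| Scenario | Last row label | Final dose (log10) | Rows in final run | Ends because | Table MTD |
|---|---|---|---|---|---|
| S1 | 18 | 9 | 10 | 10 consecutive | 9 |
| S2 | 19 | 8.5 | 10 | 10 consecutive | 8.5 |
| S3 | 20 | 8.5 | 4 | n = 20 | 8.5 |
| S4 | 20 | 8.5 | 8 | n = 20 | 8.5 |
| S5 | 20 | 9 | 8 | n = 20 | 9 |
| S6 | 20 | 9 | 7 | n = 20 | 9 |

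The 10-consecutive-or-20 rule gives the whole MTD row.

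**2. The 10% rule on the same paths.** Subjects 1 to 6 receive 5, 6, 7, 7.5, 8, 8 in every scenario. Consecutive printed doses are compared.

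- *pfu scale.* A half-log step up is 10^0.5 − 1 = +216%, and a step down is 1 − 10^−0.5 = 68%. Even a tenth-log step up is 10^0.1 − 1 = +26%. After rounding, only identical doses can qualify. The first identical pair is 8 and 8 at subjects 5 and 6, so the MTD would be 10^8 in 6 of 6 scenarios.
- *log10 scale.* 7 to 7.5 is 0.5/7 = 7.1% (6.7% of the larger value). The rule is met at subject 4, so the MTD would be 10^7.5 in 6 of 6.
- *Unrounded, log10.* Two recommendations that both round to 8 lie between 7.75 and 8.25 and differ by at most 0.5/7.75 = 6.5%. The rule is met by subject 6 at the latest.
- *Unrounded, pfu.* The same two recommendations can differ by up to 10^0.5 = 3.16-fold, so Table 2 cannot settle this reading. In a refit of the Table 1 model with no DLTs, successive uncapped recommendations still differ by about 12% at subject 20. If capped at 10^9, they first agree there, at subjects 9 and 10.

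Both readings of the printed doses stop below every MTD that the table reports.

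**3. Section 4.2's definition.** Every scenario reaches log 9. An MTD strictly below the highest dose given holds in S2, S3 and S4 (8.5 < 9) and fails in S1, S5 and S6 (9 = 9).

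**4. Six or 10 at the maximal dose.** S1 treats 10 printed rows at log 9. Its sixth is the row labelled 14. Section 4.1.1 steps the dose down after a second toxicity at the highest dose, and S1 stays at 9, so at most one of the first nine subjects there can have had a toxicity. Six would have tolerated the dose by the seventh row at the latest (label 15). Section 4.2 would stop there; Table 2 goes on to label 18.

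**5. What early declaration might cost (illustrative).** Assumed inputs: Table 1 pseudo-data, half-log rounding, 1-log cap on escalation, maximum 10^9, n = 20, true toxicity curve with slope 1 per log, 1,000 runs per setting. Each cell is the percentage of runs whose final dose is within half a log of the true 33% dose; the loss against the first row is in brackets.

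| Handling | True 10^7 | True 10^8 | True 10^9 |
|---|---|---|---|
| Run to n = 20 | 89 | 86 | 79 |
| First repeated dose, then 10 more with the CRM updating | 85 (4) | 82 (4) | 74 (5) |
| First repeated dose held for 10, then re-estimated | 86 (3) | 78 (8) | 62 (17) |
| First repeated dose, 10 more, declared dose cannot rise | 79 (10) | 58 (28) | 49 (30) |
| Stop at first repeated dose | 76 (13) | 60 (26) | 54 (25) |

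The Monte Carlo standard error of a cell is at most √(0.5 × 0.5/1000) = 1.6 points. The refit starts at 6.69 (target 0.33) or 6.71 (target 1/3), not at the 6.7842 stated below Table 1, so these are not the protocol's own operating characteristics.

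**The case against.** **Table 2 is indicative.** Section 4.1.1 says so, and it leaves room for investigator judgement and a pause with the DSMB after 10 subjects. That excuses the individual values. It does not excuse a declaration rule that, on the printed doses, fires before the reported MTD in every path shown.

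**The 10% result may be only putative.** Section 4.1.1 allows up to 10 subjects at the putative MTD, and the CRM steers de-escalation if more toxicity appears. This stands in part and greatly reduces the likely harm, as step 5 shows. It does not remove the conflict: Table 2 escalates past the point where the rule is met, and Section 4.2 closes enrolment once the MTD is determined.

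**Stronger readings that the documents do not support.** A reader might infer three.

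- *The trial would stop at 10^8 in all six scenarios.* That holds only for rounded, consecutive doses compared in pfu. The log scale gives 10^7.5, and unrounded pfu doses leave it open.
- *Section 4.2 prevents 10^9 from being the primary result.* It has a separate stop for a tolerated maximal planned dose, and the synopsis accepts that dose as the endpoint. What remains is whether that dose may be called the MTD, as Table 2 does in S1, S5 and S6.
- *The design loses 25 to 30 points of accuracy.* That requires a true dose of 10^8 or 10^9 and a declaration that either ends the trial or can never be raised.

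The cell colours marking toxicity are missing from the text available here, so tolerance by six patients cannot be checked in S3, S5 and S6.

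**Conclusion.** The conflict is real and needs correcting before the MTD is declared. It rests on the text and on Table 2's printed doses, not on the simulation. One criterion in Section 4.1.1 has no scale, rounding stage or precedence, and it contradicts the section's own worked example in 6 of 6 scenarios on either scale. Section 4.2's definition contradicts 3 of 6. The count at the maximal dose is six in one section and 10 in two others.

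The practical loss is uncertain. Under the assumed curves it runs from about 3 to 5 points, if the CRM keeps updating over the 10 further subjects, to about 30, if the declared dose is final. Confidence is high for the conflict and low for any single figure in that range.

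**What to change.** Reconcile the Study Synopsis endpoint, Section 4.1.1 (both rules and Table 2) and Section 4.2 into one rule for declaring the MTD and stopping enrolment, worded identically in each place. It should state:

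- the scale of any percentage criterion (pfu or log10), and whether it applies to recommendations before or after rounding;
- one rounding convention;
- which criterion takes precedence where more than one is kept;
- how many subjects are treated at the declared dose, and whether the CRM continues to update over them;
- whether the maximal planned dose can be reported as the MTD.

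Then re-run Table 2 so that every path follows that rule, and number its rows without a gap. Which rule is kept is for the sponsor to decide. The cost is wording in three places and a re-run of Table 2; no new data are needed.
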